6.1.5 Method of Treatment Assignment

Before starting the study, a randomization list stratified by study center will be generated. When the investigator has confirmed subject eligibility, the subject will be allocated a study product within the electronic data capture (EDC) system.

6.1.6 Kit Number/Randomization Number

A kit number/randomization number, a unique number on the label of the study products, will be assigned to each eligible subject at baseline.

 EST. 1981	Title 43QM2106 Clinical Study Protocol – QM1114 – GL	Doc id MA-49290
---	--	---------------------------

Kit number/randomization number will be allocated in ascending sequential order to each eligible subject.

6.1.7 Instructions for Use and Administration

QM1114-DP (50 U) will be compared to placebo in this study and administered based on randomization.

Placebo is identical in appearance to the active QM1114-DP but contains no active drug substance.

QM1114-DP and placebo are administered in exactly the same way. All treating investigators will be trained in the administration technique prior to the study start.

Handling of accidentally damaged or spilled study product is described in the Material Safety Data Sheet.

See also QM1114-DP IB. ¹²

6.1.7.1 *Treatment Procedure*

Prior to injection, the treatment area should be cleaned with a suitable antiseptic solution. An appropriately sized syringe and needle (e.g., 30-33 gauge needle) should be used to administer treatment.

At baseline, subjects will be randomized to receive treatment with QM1114-DP or placebo. Each treatment includes five intramuscular (IM) injections of equal volume (0.1 mL) administered at 5 injection sites in the glabellar region (0.5 mL in total). The injections should commence in the procerus muscle followed by the corrugator supercilii muscles on each side, moving outwards from the median. All injections should be approximately 1 cm above the upper orbital rim and internal to the mid-pupillary lines (Figure 2).

[figure not shown]
In order to minimize risks of regional effect of the neurotoxin (e.g., eyelid ptosis), the investigator should use one thumb to apply pressure on the upper orbital rim while injecting. It is recommended that injection is not closer than 1 cm above the central eyebrow or the bony supraorbital ridge. Moreover, the tip and bevel of the needle should always be pointed away from the study subject.

2022-03-21 13:08

Effective date:

Effective

Version: 3.0

Figure 2 Injection Sites for Treating Glabellar Lines**6.1.7.2 Post-treatment Care**

Following treatment administration, subjects will be monitored at the study center for 30 minutes.

Subjects will be instructed to avoid applying pressure, rubbing or massaging the treated area, or lying face down for 4 hours after treatment.

6.1.7.3 Treatment Regimen

Each subject will receive a single treatment with QM1114-DP or placebo at the baseline visit.

The treatments investigated in this study are:

- 50 U of QM1114-DP (0.5 mL total injection volume/0.1 mL per injection point)
- Placebo

CCI

 EST. 1981	Title 43QM2106 Clinical Study Protocol – QM1114 – GL	Doc id MA-49290
---	--	---------------------------

6.3 Supplies Management

6.3.1 Accountability

Upon receipt of the study product(s), the investigator or designee will maintain accurate records of the study product(s) delivery to the clinical study center, the inventory at the clinical study center, the use by each subject, the reconciliation of all study product(s) received from the sponsor's designee, and the return to the sponsor's designee for disposal of unused study product(s).

All study product(s) sent to the investigator/institution will be accounted for and no unauthorized use is permitted.

6.3.2 Storage of Study Product(s)

Study product(s) must be stored in a safe and secure area with restricted access, under the storage conditions specified by the sponsor (see [Table 3](#)).

6.3.3 Dispensing and Return

All study product(s) must be inventoried and a record of the dispensing for each subject must be appropriately documented. Any dispensing errors must be reported to the sponsor/contract research organization (CRO) and properly documented.

In the event of early termination/suspension of the clinical study, a rapid recall of study product(s) will be initiated.

Unused or expired study product will be returned for destruction to the sponsor representative at time points approved by the sponsor.

6.3.4 Treatment Compliance Management and Record

The treatment is an injection administered by the investigator. Details of the injection procedure will be recorded in the eCRF and subject source documents. No other measurements of treatment compliance will be made.

6.3.5 Dose Modification

Dose modifications are not permitted.

6.3.6 Product Quality Complaints

Product Quality complaints (PQCs) should be reported to the Safety e-mail listed in [Section 11.9](#). A PQC is an external judgement presuming a quality defect of a product; quality issue for a product relating to its presentation or use, identified by a subject, a practitioner or investigator site personnel, a distributor, or anyone else involved in clinical supplies handling. Examples may include but are not limited to appearance issues, odor, damaged stoppers, low fills, and foreign matter in the product. These complaints may or may not represent a potential risk to the subject. A PQC form must be completed by the study center personnel and forwarded to the sponsor or designee within 24 hours of awareness. Affected study product should be quarantined, and not used, until further notice by the sponsor.

 EST. 1981	
Title 43QM2106 Clinical Study Protocol – QM1114 – GL
	
Doc id MA-49290

---	--	-----------------------------------

Additional contact details are provided in the investigator's site file.

6.4 Blinding

This is a double-blind study in which neither the investigator, sub-investigator, study staff, nor the subject will know the subject's study product assignment (i.e., QM1114-DP or placebo). Placebo is identical in appearance to QM1114-DP but contains no active drug substance.

Subjects will be randomized at baseline to either treatment with QM1114-DP or placebo. In order to maintain the blind, the study products, QM1114-DP and placebo, will be supplied in identical vials, each with a unique number on the vial label. Both QM1114-DP and placebo will be administered in exactly the same way.

An un-blinded statistician will generate the randomization schedule; however, he/she will not be involved in any other aspect of the study prior to database lock.

The sponsor's staff or designees directly involved in clinical operations management, data management, and statistical evaluation of the study will remain blinded until the database is locked, unless emergency unblinding is required.

6.4.1 Verification of Blinding

[figure not shown]
The sponsor's staff or designees will assess and verify maintenance of the study blind during the study through routine monitoring visits.

6.4.2 Unblinding During the Clinical Study

Emergency un-blinding during the clinical study may be required for therapeutic or for regulatory reasons (for expedited safety reporting).

A blind-break system will be available for investigators. In such an emergency, the investigator will only break the blind for the subject involved.

The investigator must notify the sponsor immediately in the event of such an emergency (see contact details in Section [7.2.4.2.2](#)). If possible, the investigator should notify the sponsor before breaking the blind in order to discuss this decision with the sponsor. The investigator is required to document each case of emergency unblinding and inform the sponsor immediately.

 EST. 1981	Title 43QM2106 Clinical Study Protocol – QM1114 – GL	Doc id MA-49290
---	--	---------------------------

7. CLINICAL STUDY ASSESSMENTS

7.1 Efficacy Assessments

7.1.1 Global Aesthetic Improvement Scale

Subjects will rate the global aesthetic improvement of their GL at maximum frown, relative to their pre-treatment appearance, using the following categorical scale at all post-treatment time points through Month 12.

Rating
Very Much Improved
Much Improved
Improved
No Change
Worse
Much Worse
Very Much Worse

Subjects will be asked:

“How would you rate the change in appearance of your glabellar lines (lines between your eyebrows) at maximum frown compared with immediately before the injection?”

Subjects will be instructed to select the one rating that best describes the degree to which the appearance of their GLs at maximum frown has changed relative to baseline. The subject may review the baseline photograph to aid in the assessment.

7.1.2 Subject Diary Card

Subjects will be asked to record their assessment of study treatment response in a diary card on Days 0 through 7 post-treatment. They will be asked to respond “yes” or “no” to the following question:

“Since being injected have you noticed an improvement in the appearance of your glabellar lines (lines between your eyebrows) when you frown?”

Subjects are to complete the diary card daily, starting on the day of treatment (Day 0), and return the diary to study center at their Month 1 visit.

CCI

[figure not shown]

[figure not shown]
[figure not shown]
Effective date: 2022-03-21 13:08

Effective

Version: 3.0

CCI

 EST. 1981	Title 43QM2106 Clinical Study Protocol – QM1114 – GL	Doc id MA-49290

CCI
 		

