Effective date: 2022-03-21 13:08

[figure not shown]
Effective

Version: 3.0

SYNOPSIS	
	
randomized and dispensed the investigational product, and will be analyzed according to the randomization scheme. The ITT population will be the primary population used for efficacy analysis.
 
 • The per protocol (PP) population is a subset of the ITT subjects who complete the Month 1 visit and have no protocol deviations that are considered to have a substantial impact on the primary efficacy outcome. • The safety population includes all subjects who were administered the study product, and will be analyzed according to as-treated principle. All safety data will be summarized descriptively based on the safety population. 
CCI

Sample Size:	
Interim Analysis:	Not applicable.

2022-03-21 13:08

[figure not shown]
Effective date:

CLINICAL STUDY SCHEMATIC AND FLOW CHART**Table 1 Clinical Study Schematic***Effective*

Version: 3.0

2022-03-21 13:08

Effective date:

Figure 1 Study Flow Chart**Effective**

Version: 3.0

GALDERMA EST. 1981	Title 43QM2106 Clinical Study Protocol – QM1114 – GL	Doc id MA-49290
------------------------------	--	---------------------------

SCHEDULE OF ASSESSMENTS

Table 2 Schedule of Assessments

Visit	Visit 1	Visit 2	Visit 3	Visit 4	Visit 5	Visit 6	Visit 7	Visit 8	Visit 9	Visits 10-14	Visit 15
1 month = 4 weeks All visit windows are calculated from Baseline/Day 0		Day 0 Baseline ¹	Day 1	Day 2	Day 3	Day 4	Month 1	Month 3	Month 6	Months 7-11	Month 12/ EOS/ET ²
Window	(≤ 2 weeks of Visit 2)						(± 5 days)	(± 5 days)	(± 5 days)	(± 5 days)	(± 5 days)
Informed Consent	X										
Demographic Data ³	X										
Medical History	X										
Previous Medication/Procedures ⁴	X										
Urine Pregnancy Test ⁵	X	X ⁷									X
Focused Physical Examination ⁶	X	X ⁷	X	X	X	X	X	X	X	X	X
Vital Signs ⁸	X	X ¹⁰	X	X	X	X	X	X	X	X	X
Inclusion/Exclusion Criteria	X	X ⁷									
Photography		X ⁷	X	X	X	X	X	X	X	X	X
CCI											
Blood sample for serum antibody testing		X ⁷					X		X		
Randomization		X ⁷									
Treatment		X									
Dispense Subject Diary Card		X									
Collect Subject Diary Card							X				
Adverse Events	X	X ¹⁰	X	X	X	X	X	X	X	X	X
Concomitant Medication/Procedures	X	X ¹⁰	X	X	X	X	X	X	X	X	X
SUBJECT ASSESSMENTS											
CCI											
GAIS			X	X	X	X	X	X	X	X	X
INVESTIGATOR ASSESSEMENTS											
CCI											

CONFIDENTIAL
Page 18 of 86

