2.1.2 Secondary Efficacy Objectives and Endpoints

The secondary efficacy objectives and endpoints of the study are:

[figure not shown]
1. To evaluate onset of treatment effect following a single dose of QM1114-DP and placebo as assessed by the subject using the diary card on Days 0 through 7 post-treatment.

Endpoint: Onset of effect is defined as the first day a subject answers “yes” to the diary question.

2. To evaluate aesthetic improvement following a single dose of QM1114-DP and placebo as assessed by the subject using the GAIS at maximum frown at all applicable time points.

Endpoint: Responder rate based on the 7-point GAIS. A responder is defined as a subject who responds at least “Improved” on the GAIS at maximum frown.

CCI

[figure not shown]

Effective date: 2022-03-21 13:08

Effective

Version: 3.0

CCI

 EST. 1981	Title 43QM2106 Clinical Study Protocol – QM1114 – GL	Doc id MA-49290
---	--	---------------------------

CCI

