8.1.5 Month 1/Visit 7 (\pm 5 days)

The investigator or designee will:

1. Ask the subject about AEs using an open-ended question, such as “Have you noticed any change in your health since the last visit?” Record all events, as appropriate.
2. Ask the subject about any changes in his/her concomitant therapies/procedures (added, removed or changed) since the previous visit. Record all changes.
3. Collect the subject’s diary and review for completion.
4. Take subject photographs (refer to photo manual for complete instructions). If the subject is wearing make-up, instruct the subject to remove it prior to taking photographs.
5. **CCI**
[REDACTED]
6. Collect blood sample for neutralizing antibody testing (Section [7.2.3](#)).
7. **CCI**
[REDACTED]
 (Section [7.1.7](#)).
8. Review GAIS completion instructions with the subject. Subject to complete the GAIS (Section [7.1.1](#)).
9. **CCI**
[REDACTED] ([Appendix 1](#)).
10. **CCI**
[REDACTED] ([Appendix 2](#)).
11. **CCI**
[REDACTED] ([Appendix 3](#)).
12. **CCI**
[REDACTED] ([Appendix 4](#)).
13. Obtain the subject’s vital signs (blood pressure, heart rate, and respiratory rate). Vital signs are to be taken seated after 10 minutes rest (Section [7.2.2](#)).
14. **CCI**
[REDACTED] ([Section 7.1.8](#) and [Appendix 5](#)).
15. Investigator to perform a FPE ([Appendix 7](#)).
16. **CCI**
[REDACTED] ([Appendix 6](#)).
17. Schedule the next visit (Month 3/Visit 8).

CONFIDENTIAL

Page 57 of 86

GALDERMA <small>EST. 1981</small>	Title 43QM2106 Clinical Study Protocol – QM1114 – GL	Doc id MA-49290
---	---	----------------------------------

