8.3 Subject Instructions

Subjects will be instructed to complete a diary card daily, Day 0 through Day 7, following treatment with study product, and return the diary to the study center at their Month 1 visit.

Subjects will be advised that any facial make-up will need to be removed before taking study photographs.

Subjects will also be advised of post-treatment care instructions as outlined in Section 6.1.7.2.

GALDERMA <small>EST. 1981</small>	Title 43QM2106 Clinical Study Protocol – QM1114 – GL	Doc id MA-49290
---	---	----------------------------------

Effective date: 2022-03-21 13:08

Effective

Version: 3.0

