1.3.2 Subject Diary Card

Subjects will be asked to record their assessment of study treatment response in a diary card on Day 0 (baseline post-treatment) through Day 7. They will be asked to respond “Yes” or “No” to the following question:

- *“Since being injected have you noticed an improvement in the appearance of your glabellar lines (lines between your eyebrows) when you frown?”*

Subjects will complete the diary card daily, starting on the day of treatment (Day 0), and will return the diary to study site at their Month 1 visit.

For each subject, time, in days, to onset of treatment response will be computed. A flag will be created to determine the diary date of when the subject first answers 'Yes' to "Since being injected have you noticed an improvement in the appearance of your glabellar lines (lines between your eyebrows) when you frown?" Time, in days, to onset of treatment response will be calculated as follows:

$$\text{Number of days to onset} = \text{Date of Diary Flag} - \text{Date of Day 0}$$

Subjects who never notice an improvement will be censored at Day 7. Subjects dropping out before noticing improvement will also be censored at Day 7 or date of withdrawal, whichever comes first. Subjects who never return their diary will be censored on Day 7.

[figure not shown]
CCI

Sponsor: *Galderma*

Protocol Number: *43QM2106*

Plan Version: *V1.0*

CCI

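### The onset diary for Days 0 to 7 is not checked until Month 1, 16 to 26 days after its last entry, although subjects attend clinic on Days 1, 2, 3 and 4

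*Protocol*

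**What the plan says.** **Endpoint.** Protocol 2.1.2 lists onset as the first secondary objective: "Onset of effect is defined as the first day a subject answers" yes to the diary question. The answers are recorded "in a diary card on Days 0 through 7 post-treatment" (Protocol 7.1.2). Onset is also in the study title and in the clinical hypothesis (Protocol 2.2).

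**Handling of the card.** It is dispensed at baseline with instruction on how to complete it (Protocol 8.1.2). Subjects are to fill it in daily "and return the diary to study center at their Month 1 visit" (Protocol 7.1.2). They are again told to "return the diary to the study center at their Month 1 visit" (Protocol 8.3), and SAP 1.3.2 likewise says that they "will return the diary to study site at their Month 1 visit". The first site action after dispensing is step 3 of the Month 1 visit (Protocol 8.1.5), where staff collect the subject's "diary and review for completion". Protocol Table 2 and SAP Appendix A carry one dispensing mark, at Visit 2, and one collection mark, at Visit 7.

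**Visits in between.** Subjects attend on Days 1, 2, 3 and 4 (Protocol 8.1.3 and 8.1.4). The readable steps cover adverse events, concomitant therapies, photographs, GAIS, vital signs and the focused physical examination. None mentions the diary.

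**Analysis.** Time to onset is summarised by Kaplan-Meier methods with a median (Protocol 9.1.3). Endpoints other than the primary are descriptive (Protocol 9.1.5; SAP 2.4.5.1). SAP 1.3.2 censors a subject whose diary never comes back at Day 7.

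**The concern.** The endpoint is resolved in single days over one week, so its value depends on each entry being made on its own day. The plan tells subjects to do this but describes no way of confirming it: no interim check, reminder, time stamp or rule for late entries. A card completed shortly before Month 1, when the subject already knows how the treatment turned out, would pass the completion review just as a card kept daily would. A gap found at Month 1 cannot then be filled with a same-day answer.

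A lost card is a separate problem. Censoring at Day 7 keeps the subject in the risk set for the whole week as though onset had been looked for and not found. Nothing was in fact observed. This pulls the reported onset curve down and can delay its median.

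Both risks could be reduced cheaply, because the subject is in clinic on four of the eight diary days.

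**Working it through.** No figure in the plan bears on this, so there is none to reproduce. The check is date arithmetic, followed by the effect of the censoring rule.

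**Step 1: when the card is first seen.** Table 2 states "1 month = 4 weeks" and "All visit windows are calculated from Baseline/Day 0", and the Month 1 window is ± 5 days.
- Month 1 = 4 × 7 = Day 28; with the window, 28 − 5 = Day 23 to 28 + 5 = Day 33.
- From the Day 7 entry: 23 − 7 = 16 days to 33 − 7 = 26 days; nominally 28 − 7 = 21 days, or three weeks.
- From the Day 0 entry: 23 to 33 days.
- From the Day 4 visit, the last clinic contact before Month 1: 23 − 4 = 19 to 33 − 4 = 29 days.

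**Step 2: what existing visits could verify.** There are eight entries. Those for Days 0 to 3 are due by the Day 4 visit. The Day 4 entry is also available if it is made before the visit, but Protocol 7.1.2 sets no time of day. So four or five of eight entries can be checked, each within about a day. The Day 5, 6 and 7 entries cannot.

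**Step 3: effect of unreturned cards.** Let F(t) be the true proportion with onset by day t and q the share of cards not returned. Assume that loss is unrelated to onset, that returned cards are complete, and that nobody withdraws in the week. Every lost card stays at risk through Day 7 without an event, so the Kaplan-Meier onset curve on Days 0 to 7 is (1 − q) × F(t). The reported median is the first day on which F(t) ≥ 0.5 / (1 − q). The documents give no loss rate; the values of q below are assumptions.

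| Assumed q | QM1114-DP cards lost (of 90) | Placebo cards lost (of 30) | True onset needed for the median |
|---|---|---|---|
| 0% | 0 | 0 | 50% |
| 5% | 4.5 | 1.5 | 0.5 / 0.95 = 52.6% |
| 10% | 9 | 3 | 0.5 / 0.90 = 55.6% |
| 20% | 18 | 6 | 0.5 / 0.80 = 62.5% |

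Whether this moves the median depends on the curve. As an illustration, assume 52% onset by Day 2 and 70% by Day 3. With no loss the median is Day 2. With 5% loss the curve shows 0.95 × 52% = 49.4% at Day 2 and 0.95 × 70% = 66.5% at Day 3, so the median becomes Day 3. A curve that is not close to 50% on any day would not shift at this loss rate.

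**Step 4: effect of late entries.** This cannot be calculated. The documents give no readable expected onset time, back-filling rate or recall error. Back-filling could move onset in either direction.

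**The case against.** The strongest reply is that little depends on this. Onset is a secondary endpoint with descriptive analysis, no planned between-arm test uses the diary, and the Month 1 GAIS comparison is untouched. This stands, and it limits the weight of the point.

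Second, early effect is also recorded at the time. Subjects rate GAIS in clinic on Days 1 to 4, and responder rates are shown by visit and arm with confidence intervals (SAP 2.4.5.3). This also stands: an implausible diary onset could be compared with those ratings. But the onset endpoint does not use them, and the plan does not specify the comparison.

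Third, the plan is not silent. Daily completion is instructed, Month 1 is the first scheduled visit after the diary ends, and unreturned cards have a rule. The rule shows that loss was foreseen, but it assigns follow-up that did not take place.

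Fourth, several visit steps are blacked out, so a diary check might be hidden. That is unlikely, because the diary is legible wherever else it appears and the schedule marks a single collection.

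A reader might go further and infer that recall error is as large as the onset time itself, or that it differs between arms because treated subjects reconstruct an onset and placebo subjects do not. The documents support neither. They contain no recall-error figure and no evidence on how either arm would complete a card late.

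**Conclusion.** The point holds as a low-cost improvement to data quality. A titled objective measured in single days rests on entries that no readable step checks until 16 to 26 days after the last of them, and a card that is not returned counts as seven days observed without onset.

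Only the loss component can be sized. Under the stated assumptions, 5% to 20% loss raises the onset proportion needed for the median from 50% to between 52.6% and 62.5%. The direction is toward later apparent onset, not toward flattering the product. The back-filling component is a possibility that the design leaves open; its frequency, size and direction are unknown. It would be wrong to read this as showing that the onset result is biased in favour of QM1114-DP or that the primary conclusion is at risk.

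The verdict assumes that the blacked-out steps contain no diary check. It also takes the specific Day 7 rule in SAP 1.3.2 to govern unreturned cards, ahead of the general observed-cases wording in SAP 2.4.5.1.

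**What to change.** **Protocol 8.1.3, 8.1.4 and Table 2 (Visits 3 to 6).** Add a step along these lines: *Subject brings the diary. After all subject and investigator assessments, a staff member who does not perform efficacy assessments confirms that an entry exists for each day due, and initials and dates the card.* At Day 4 the same staff member keeps a copy, which is not shown to the assessing investigator, and reminds the subject to complete Days 5 to 7.

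**SAP 1.3.2.** If the card is not returned, use the Day 4 copy. Censor a subject with no yes answer at the last verified entry instead of at Day 7. With this rule, and loss unrelated to onset, the (1 − q) factor disappears over the copied days; in the illustration above the median returns to Day 2. The section should also say what happens when there is neither card nor copy. By the same reasoning, that subject contributes no observed days.

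**Cost and limits.** A few minutes at four visits already scheduled, one added procedure step, and one changed SAP rule. No new visits are needed. There is a small risk that site staff see the subject's answers before Month 1, which the ordering and the separation from assessors limit. Four or five of the eight entries become verifiable; Days 5 to 7 remain unverified until Month 1.
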